7. DATA COLLECTION AND MEASUREMENTS

Data collection contact schedule

Eligibility, baseline, and follow-up data will be collected by phone, through mailings, and at in-person visits. In-person data collection visits will primarily be conducted at the ProHealth Clinical Research Unit in Woodlawn, MD. In general, we try to be as flexible as possible to meet the needs of our participants. For example, we might divide or bundle data collection across visits. See Table below for an overview of proposed data collection items by visit. Some items might be dropped based upon participant burden, scientific considerations, available resources, and the results of field testing. The primary data collection points for participant-level data are as follows:

Pre-Screen Contact (PS) – A brief questionnaire will be administered by phone to identify potentially eligible participants quickly and efficiently.

Screening Visit 1 (SV1) – This in-person visit will include written informed consent for screening, questions about medical history, medications, and eligibility; serum collection for uric acid screening and urine specimen collection.

Screening Visit 2 (SV2) – This in-person visit will include further questions about demographic characteristics, baseline diet, physical activity, gout, and global pain. We will also measure height and weight and perform seated and standing blood pressure assessments (BP and OH), and a “Timed Up and Go” (TUG) test.

Randomization Visit (RZ) – This in-person visit will include additional questionnaires on physical activity, a repeat weight assessment, measurement of BP and OH. Participants will be provided an opaque envelop to learn the intervention sequence. They will subsequently be provided instructions on the next phase of the study.

Feeding Period 1 Visit (FP1) – This in-person visit includes diet screening, a medication questionnaire, physical activity questionnaires, pain assessments, and questions about adverse effects from diet, compliance, and palatability. In addition, we will perform phlebotomy, urine assessments, and physical examinations including weight, BP, OH, and the TUG test. Participants will also receive instructions for their next feeding assignment.

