Feeding Period 2 Visit (FP2) – This in-person visit includes diet screening, a medication questionnaire, a physical activity questionnaire, a pain assessment, a questionnaire about adverse effects from diet, compliance, and palatability. In addition, we will perform phlebotomy, urine assessments, and physical examinations including weight, BP, OH, and the TUG test. We will also provide participants with some close-out materials including a certificate of appreciation.

Table. Data Collection Schedule

	Pre-	Screening/Baseline/Randomization			Feeding Periods Period	
	screen PSV	SV1	SV2	RZ	FP1	FP2/Close-out
Pre-screen questionnaire	✓					
Study description/instructions	✓	✓		✓		
Informed consent		✓				
Randomization assignment				✓		
Eligibility checklist		✓	✓			
Medication list questionnaire		✓	✓	✓	✓	✓
Medical history		✓				
Demographic questionnaire			✓			
Physical activity questionnaire (for Calorie estimator)			✓	✓	✓	✓
Gout questionnaire			✓			
Global pain and function questionnaire			✓		✓	✓
Diet compliance					✓	✓
Diet palatability/Symptom/diet tolerance questionnaire (DD intervention only)					✓	✓
Interim event			✓	✓	✓	✓
Diet screener (fruit/vegetables/fat)			✓		✓	✓
Serum collection		✓			✓	✓
Urine collection		✓			✓	✓
Seated blood pressure			✓	✓	✓	✓
Orthostatic hypotension			✓	✓	✓	✓
Height			✓			
Weight			✓	✓	✓	✓

TUG test			✓		✓	✓
Close-out survey with certificate						✓

Note: During the DASH intervention, participants will complete weekly food ordering calls with the study dietitian. Grocery orders will be documented.

Measurements

Primary outcome variable.

Uric acid. Fasting blood will be collected during SV1, FP1, and FP2 for SUA, blood glucose, total cholesterol (TC), HDL cholesterol (HDL-C), and triglycerides. LDL-C will be estimated by the equation (LDL=TC-HDL-triglyceride/5).

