2. Bruising and a rare chance of local infection from venipuncture to collect blood samples could occur.
3. There might be loss of confidentiality and privacy.
4. Change in uric acid levels could precipitate a gout flare

Adverse event surveillance and reporting procedures

The OHRP defines an adverse event as “Any untoward or unfavorable medical occurrence in a human subject, including any abnormal sign, symptom, or disease, temporally associated with the subject's participation in the research, whether or not considered related to the subject's participation in the research.”

We will monitor for adverse and other relevant clinical events associated with study participation during in-person visits. In addition, it is possible participants may report events during grocery ordering calls (phone contact). A study clinician will review completed forms and labels and take appropriate action for any abnormal clinical values or reports of medical conditions. Serious events thought to be secondary to the study intervention will be reviewed by the investigative team of 4 physicians, during our weekly trial meeting.

The trial operation will be organized into teams of investigators and staff. The primary decision making body for the trial operation will be the Oversight Committee, chaired by the PIs ([name] and [name]) and comprised of all investigators and senior staff. This committee will convene monthly, review the progress of all components, and focus on high-level scientific and administrative issues.

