- Rigorous training of clinic staff emphasizing the importance of:
 - Positive and warm interpersonal relationships between the participants and study staff
 - Study commitment during the consent process to ensure that potential participants understand the importance of completing the study
 - Addressing participant concerns to minimize dissatisfaction
 - Collecting data even if a participant discontinues the study treatment

Reasons for any drop-outs will be documented. If a drop-out occurs for reasons related to the study, i.e., informative censoring, we will perform sensitivity analyses using established methods for addressing informative censoring, namely, imputation techniques for missing data, best and worst-case scenarios, and use of the drop out event as a study end-point.⁹ We will review these approaches to minimize bias. Further, we will compare the baseline characteristics of participants with missing measures between the two assignments.

6 Safety outcomes

We will compare the rate of gout flares by assignment group using Poisson regression. We will also compare self-reported symptoms that are thought to potentially arise from the diets.

7 References

2. Senn SS. *Cross-over Trials in Clinical Research*. Second. John Wiley & Sons, Ltd; 2002.

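### The schedule restricts the symptom form to the DASH phase, and gout severity (endpoint G) has no follow-up form or cut-off, yet the SAP plans to compare symptoms and to test G between phases

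*SAP*

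**What the plan says.** **Symptoms.** SAP section 6 (Safety outcomes) has two sentences. The first is "We will compare the rate of gout flares by assignment group using Poisson regression"; the second is "We will also compare self-reported symptoms that are thought to potentially arise from the diets". The second names no form, visit, model or comparator. A comparison between phases is the natural reading, given the sentence before it.

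The Protocol section 7 schedule has one row for symptoms, ticked at FP1 and FP2: "Diet palatability/Symptom/diet tolerance questionnaire ( DD intervention only". No other row carries that restriction. The visit text in the same section lists, for FP1, "questions about adverse effects from diet, compliance, and palatability" and, for FP2, "a questionnaire about adverse effects from diet, compliance, and palatability". Neither is limited by phase. The section introduces the table with "See Table below for an overview of proposed data collection items by visit" and does not say whether table or text governs.

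**Gout severity.** SAP 3.5 lists G as a binary endpoint, tested between phases by GEE with baseline adjustment. The schedule ticks the gout questionnaire at the second screening visit (SV2) only, and Protocol section 7 describes the form as covering gout history. The FP1 and FP2 text mentions pain assessment but no gout form. The only severity rule in the SAP is in 3.4 (Pre-specified Stratified Analysis), where baseline flare count is split at its median to form subgroups.

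**The concern.** A symptom comparison needs the same questions asked in the same way after each diet. If the table is followed, participants answer a dedicated symptom form after DASH and not after the self-directed phase. What remains for the self-directed phase is the interim-event form and general adverse-event monitoring at visits. Neither is described in enough detail to show that it asks the same things. A difference in reported symptoms could then reflect the instrument as well as the diet.

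For G, the plan specifies a model but neither the measurement nor the threshold that turns it into a binary outcome. If these are chosen after collection from several candidate forms, the analyst has a freedom that a pre-specified plan is meant to remove. The baseline adjustment has the same gap: a gout-history form at SV2 is not obviously the baseline counterpart of a severity measure covering a 4-week phase.

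**Working it through.** The plan gives no figure to reproduce here, so the check sets the schedule against the visit text and the SAP.

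**Inputs.** 40 participants and two phases each (Protocol sections 4 and 12; SAP section 1); schedule ticks over six contacts, namely pre-screen, SV1, SV2, randomization (RZ), FP1 and FP2 (Protocol section 7). Full retention is assumed.

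**Step 1: symptom forms.** Phase-visits: 40 × 2 = 80, of which 40 are DASH and 40 self-directed.

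| Source followed | DASH forms | Self-directed forms |
|---|---|---|
| Schedule table | 40 × 1 = 40 | 40 × 0 = 0 |
| FP1/FP2 visit text | 40 × 1 = 40 | 40 × 1 = 40 |

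Under the table, about 20 of the 40 DASH forms fall at FP1 and about 20 at FP2. The split is approximate because SAP 3.1 promises only about half in each sequence and the block sizes vary. A period 1 analysis would have about 20 forms against 0.

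**Step 2: candidate sources for G.**

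| Form | Contacts ticked | Of 6 | Of 2 feeding visits | Assigned to G? |
|---|---|---|---|---|
| Gout questionnaire | SV2 | 1 | 0 | No |
| Global pain and function | SV2, FP1, FP2 | 3 | 2 | No |
| Interim event | SV2, RZ, FP1, FP2 | 4 | 2 | No |

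Gout questionnaires scheduled for the phase outcomes: 80 × 0 = 0. Here the table and the visit text agree. The SV2 text names gout and global pain separately, while the FP1 and FP2 text names pain only.

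**Step 3: can G be inferred from what is collected?** The pain form runs at both feeding visits, and Protocol section 7 says that the gout and pain forms draw on common source scales. But joint pain and physical function are already endpoints I and H, and no section links the pain form to G. The interim-event form runs in both phases, but its content is not described. The median-flare split applies to baseline subgroups; nothing extends it to a 4-week outcome. The scope of G also varies: SAP 1.2 couples severity with flares, while SAP 3.5 and the Protocol's aims list severity alone.

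**The case against.** The strongest reply on symptoms is that the conflict rests on one parenthetical label. Both visit descriptions, and the SAP's plural reference to diets, are compatible with collection in both phases. The label follows a three-part row name and might be meant for only part of it, and the table is offered as an overview. The case report forms and the manual of procedures, which were not available, might settle this and the source for G. This stands as far as it goes: the documents do not show that data are missing. They do show two incompatible instructions for the one form that the comparison needs. The reply does not supply a source or cut-off for G. It is also fair that G is one of twelve other aims.

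Four stronger readings are tempting and should not be drawn.

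- A reader might infer that self-directed symptoms would be merely volunteered. The interim-event form and visit monitoring run in both phases, and nothing shows that they do not prompt for symptoms.
- A reader might infer a reporting bias from contact frequency, because "During the DASH intervention, participants will complete weekly food ordering calls with the study dietitian" and Protocol section 11 says "it is possible participants may report events during grocery ordering calls (phone contact". That is an opportunity to report, not a collection procedure, and SAP section 5 also plans reminder contacts and a 24-hour telephone line without limit by phase.
- A reader might infer that a DASH-only form reveals the phase to masked staff. The documents state neither who gives it nor when in the visit.
- A reader might take the Poisson flare analysis to be either affected or safe. No section names the source of the flare counts, so neither follows.

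**Conclusion.** The point holds as one conflict between passages and one missing definition.

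1. Following the schedule leaves 40 DASH symptom forms against 0 self-directed forms; following the visit text gives 40 and 40. In the first case the planned comparison would rest on different instruments and may not be like for like.
2. None of the 80 phase outcomes for G has a gout questionnaire scheduled. No other form is assigned, and no threshold for a severe case is stated.

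The counts assume 40 participants with full retention. The size of any resulting bias cannot be computed from the documents. The textual findings are firm; the consequences depend on which instruction was followed in the clinic. The primary serum uric acid analysis is unaffected. The change should be made, but it does not threaten the trial's main conclusion.

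**What to change.** **Symptoms.** Reconcile the table with the visit text by removing the DASH-only limit from the symptom and tolerance items, so that identical items with a 4-week recall are given at FP1 and FP2 in both phases. Palatability of study food can stay DASH-only. State in SAP section 6 that the comparison is between phases and uses those items only. If self-directed symptoms were not collected, report DASH symptoms descriptively, without a comparison.

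**Endpoint G, if visits remain.** Collect the same gout severity items with a 4-week recall at FP1 and FP2, and state the cut-off. Add a matching pre-randomization item for those still to be randomized. Where no matching baseline is available, analyse G without baseline adjustment and say so.

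**Endpoint G, if collection is complete.** The SAP is dated May 20, 2019 and the timeline ends in June 2019, but actual status is not stated. Before unmasking, choose one of two courses:

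- define G from a form already collected at baseline and at FP1/FP2 (interim event, or pain and function), with a stated cut-off, noting the overlap with the flare analysis or with H and I; or
- drop G from between-phase testing.

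**Cost.** A few questionnaire minutes per visit, with no new visits or procedures. Items added late leave partial data for participants who have already completed a phase. If collection is finished, the cost is SAP text, plus loss of the symptom comparison if self-directed forms do not exist.

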5. STUDY POPULATION AND ELIGIBILITY

Eligibility criteria are summarized below. This trial focuses on gout in the setting of no active ULD use. Given potential potassium overloading from the DASH diet, we will exclude patients with hyperkalemia or CKD stage 4 or higher, similar to previous DASH trials, although the DASH diet is even expected to slow the progression of CKD.

Inclusion criteria:

- Age 18-100 years
- Self-reported gout diagnosis
- Serum Uric Acid ≥ 7 mg/dL

Exclusion criteria:

- Unstable or Stable ULD use or plans to initiate ULD
- Patients with hyperkalemia (>5 mmol/L)
- Consumption of more than 14 alcoholic drinks per week or more than 6 alcoholic drinks in one occasion
- Chronic kidney disease (GFR < 30 cc/min), active dialysis, or history of kidney transplant
- Inability to give informed consent
- Chronic steroid use, warfarin use, insulin use
- Unstable lipid, diabetes, and hypertension medication use (2 month period)
- Active heart attack, heart failure, angina, coronary bypass, COPD
- Active cancer or cancer treatment
- Active inflammatory bowel disease, malabsorption, history of major gastrointestinal surgery involving bowel resection
- Pregnant, plan to become pregnant, or breast feeding
- Plans to leave geographic area in the next 3 months
- Active participation in another clinical trial
- Significant food allergies, preferences, or intolerances
- Unable to give informed consent
- Unable to pick up foods at the research clinic during the DASH intervention phase
- Unable to transport or store food properly, lack of a cooking facility at home Terminal or mental illness

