Clinical Blood Pressure. Clinical blood pressure (BP) will be determined by the OMRON 907XL. This device records BP using an oscillometric technique. The OMRON device has been validated against the mercury random zero. BP is obtained by trained and certified data collectors according to a standard protocol, adapted from the protocol used in the Omni-Heart trial. Three measurements (each separated by 30 seconds) are obtained at each visit on the right arm of participants after they rest quietly in the seated position for at least 5 minutes. A cuff of appropriate size is identified at the initial visit and used thereafter at all subsequent visits. Heart rate is also recorded by the OMRON device. We will repeat this assessment immediately after standing to assess BP regulation (orthostatic hypotension). BP will be measured at SV2, RZ, and both FPs. The average BP of SV2 and RZ will be used to estimate baseline BP. The average BPs measured after each 4-week period will be used to determine intervention effects on BP.

Secondary outcome variables.

- a. Urinary sodium and potassium and creatinine excretion. Spot urine collections, urinary sodium (Na), potassium (K), and creatinine excretion will be used to estimate group compliance with dietary aspects of the intervention (i.e., sodium excretion for salt intake and potassium excretion for fruit and vegetable intake). We will also measure urine pH and uric acid to explore the effects of the diets on urine excretion of uric acid as a potential mechanism for serum urate reduction.
- b. Other serum measures. While no specimens will be banked, we will measure serum sodium, potassium, chloride, bicarbonate, and transaminase levels as part of an extended metabolic panel used to determine uric acid levels.

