11. SAFETY

Safety monitoring

The study will monitor participant safety. One aspect of safety monitoring is to evaluate screenees to determine whether it is safe for them to participate. Key safety related eligibility criteria are the exclusion of persons with baseline hyperkalemia or chronic kidney disease as the DASH diet is a higher potassium diet.

In addition, while risk from the diet is anticipated to be minimal we will be obtaining clinical data, specifically blood pressure and lab values, and it is possible to detect abnormal clinical values unrelated to the study. All labs will be reviewed by a study physician. Any critically abnormal values will be communicated immediately to participants and permission will be obtained to communicate directly with their primary care provider (PCP). Values that are mildly abnormal will be communicated via letter with encouragement to follow-up with their PCP. With regards to blood pressure, if systolic blood pressure is >180 mm Hg or diastolic blood pressure is >110 mm Hg, we will notify the study physician and advise the participant to follow-up with their primary care provider within 7 days. If systolic blood pressure is >160, but ≤180 mm Hg or if diastolic blood pressure is >100, but ≤110 mm Hg we will advise participants to follow up with primary care provider within 1 month.

We will also monitor participants for gout flares (a health condition related to our intervention) and for medical conditions unrelated to our intervention. If a participant develops a medical problem this will be reviewed by the study physician and discussed with the participant's PCP.

Our study will have a designated study clinician who will review medical eligibility criteria, clinical measures, and laboratory reports. This individual will also serve as the primary contact for staff, participants, and their PCPs regarding medical issues.

The study clinician will also be responsible for reviewing and reporting any adverse events for the site. This person or persons will have appropriate back-up during vacations or other absences to provide 24/7 medical safety coverage for the duration of the study.

Potential risks

This study should not involve any major risk to screenees and trial participants. However, there are some potential risks associated with participation in this study, which are as follows:

1. Participants may be uncomfortable with certain questions on the questionnaires.

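### Serum potassium, the laboratory measure of a hazard the protocol itself names, is collected after each diet phase, but the SAP plans no comparison of it between diets

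*SAP*

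**What the plan says.** **The hazard.** Protocol section 5 states: "Given potential potassium overloading from the DASH diet, we will exclude patients with hyperkalemia or CKD stage 4 or higher". The cut-off in the exclusion list is above 5 mmol/L. Protocol section 11 repeats the reasoning, giving as key safety criteria the "exclusion of persons with baseline hyperkalemia or chronic kidney disease as the DASH diet is a higher potassium diet". The same section names a second intervention-related hazard: "We will also monitor participants for gout flares (a health condition related to our intervention"). Its list of potential risks includes "Change in uric acid levels could precipitate a gout flare".

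**The measurement.** Protocol section 7, item b under the secondary outcome variables, says "we will measure serum sodium, potassium, chloride, bicarbonate, and transaminase levels as part of an extended metabolic panel used to determine uric acid levels". On timing, the same section says "Fasting blood will be collected during SV1, FP1, and FP2 for SUA" and several other assays.

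**The analysis.** SAP sections 1.2 and 3.5 list outcomes A to L. Potassium appears once, in item E, as urinary excretion. SAP section 6 has two sentences: gout flares are compared by Poisson regression, and "We will also compare self-reported symptoms that are thought to potentially arise from the diets".

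**The concern.** Of the two intervention-related hazards the protocol names, gout flare has a planned comparison between diets and potassium has none, although the data for it should be in hand. The protocol classes serum potassium with its secondary outcome variables, and the SAP does not carry it forward.

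The two planned safety comparisons cannot stand in for it. A rise in serum potassium may produce no symptom for a participant to report, and flares concern uric acid. Urinary potassium does not fill the gap either: Protocol sections 7 and 10 use it as a measure of adherence, so it reflects intake and not the serum level.

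At stake is what the trial can say about the tolerability of the diet. If the SAP is followed as written, any safety statement would rest on flares and symptoms, and whether the potassium data are compared at all would be decided after the results are known. Excluding patients at baseline does not answer the question for those enrolled. Only GFR below 30 is excluded, so participants with GFR from 30 to 59 can enter, and the SAP's stratified analyses (section 3.4) include eGFR below 60 as a subgroup for uric acid.

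**Working it through.** The plan states no figure on this point, so there is none to reproduce. The check has two parts.

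**1. Tracing serum potassium through the documents**

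| Step | Place | Finding |
|---|---|---|
| Named as a hazard | Protocol 5 and 11 | Yes; basis of key exclusions |
| Measured | Protocol 7, item b | Yes, in the panel used for uric acid |
| Timing | Protocol 7, uric acid paragraph | Blood at SV1, FP1 and FP2 |
| Classed as an outcome | Protocol 7 | Under secondary outcome variables |
| SAP endpoints A to L | SAP 1.2 and 3.5 | Absent; urinary potassium only |
| SAP safety analysis | SAP 6 | Absent; flares and symptoms only |

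One step is an inference. The sentence on timing lists uric acid, glucose and lipids but not potassium. Because item b says potassium comes with the panel that yields uric acid, values at SV1, FP1 and FP2 follow. The inference is sound, but the schedule does not state it outright.

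**2. What the existing data could show**

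Inputs: n = 40 participants (Protocol 12), taken as 40 complete pairs. The documents give no SD for serum potassium, so I assume a within-person SD of 0.3 to 0.4 mmol/L.

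*Mean difference.* The SD of a paired difference is √2 × within-person SD:
- √2 × 0.3 = 0.424
- √2 × 0.4 = 0.566

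The 95% half-width is t(0.975, 39) × SD of difference / √40, with t = 2.023 and √40 = 6.325:
- 2.023 × 0.424 / 6.325 = 0.136 mmol/L
- 2.023 × 0.566 / 6.325 = 0.181 mmol/L

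As a wider range, setting the SD of the difference directly at 0.3 to 0.6 mmol/L gives half-widths of 0.10 to 0.19 mmol/L.

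*Counts above 5 mmol/L.* With no case among 40, the exact two-sided 95% upper limit is 1 − 0.025^(1/40) = 0.088, or 8.8%. The chance of seeing at least one case is 1 − (1 − p)^40, for an assumed true rate p:
- p = 1%: 33%
- p = 2%: 55%
- p = 5%: 87%

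The mean difference can therefore be estimated with useful precision. The counts cannot exclude a rate of several per cent, and counts within eGFR below 60 would say less still, since that subgroup's size is unknown.

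**The case against.** The case on the other side has four parts.

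*The protocol already covers it.* Protocol section 12 extends the primary approach to other outcome variables, and section 7 lists serum potassium among the secondary ones. Nothing says that the SAP's list is exhaustive. This is a fair reading, and it narrows the defect: a protocol variable was not carried into the SAP. But the sentence in section 12 names no outcome, and the SAP, which does name them, lists twelve without this one. No comparison is specified.

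*Potassium is handled clinically.* Patients with hyperkalemia or GFR below 30 are excluded, a study physician reviews all laboratory results, and critically abnormal values are communicated at once. This stands. A reader might infer from the missing analysis that participants are unprotected or the values ignored; Protocol section 11 shows otherwise. Individual review still yields no estimate of the diet's effect, and Protocol section 9 keeps the order of diets from the investigators until data collection ends.

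*The hazard is not the main one.* A reader might infer that potassium overload is the only, or the chief, toxicity the protocol names. The documents do not support that. Gout flare is also called intervention-related and is analysed, and potassium is not on the list of potential risks in Protocol section 11.

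*No safety claim is planned.* Neither document sets a safety aim or promises a conclusion that the diet is safe. This also stands: the concern is what a later safety statement would leave out, not that such a statement has been written.

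**Conclusion.** The omission is real and minor. Serum potassium measures a hazard that the protocol names and builds exclusions on. It should be available at baseline and after each phase, yet neither the SAP's endpoints nor its safety section compares it between diets. The primary estimate, its test and its power are untouched.

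A paired comparison of 40 participants would give the mean difference to within about ±0.14 to ±0.18 mmol/L. This rests on the assumed within-person SD of 0.3 to 0.4 mmol/L and on complete pairs. It would be tempting to judge that interval against 5 mmol/L, but the documents do not support doing so: the figure is an eligibility cut-off for an individual, "Patients with hyperkalemia (>5 mmol/L"), not a margin for a mean change. How many participants exceed it is a separate question, on which 40 participants give only descriptive evidence.

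**What to change.** Add to SAP section 6:

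1. The within-person DASH minus self-directed difference in end-of-period serum potassium, with its 95% CI, from the same model as the primary outcome and adjusted for the SV1 value.
2. The number of participants above the protocol's own eligibility cut-off of 5 mmol/L at the end of each phase, overall and, if numbers allow, for eGFR below 60. Label these counts as descriptive and give exact confidence limits.

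It would also help to state in the Protocol section 7 schedule that the metabolic panel is drawn at SV1, FP1 and FP2.

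The cost is a few lines of text and one more model. No new samples or visits are needed, and clinical management does not change. The only downside is one more safety comparison, which should be reported as an estimate and not as a test of a hypothesis.
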